11.0 Other Analyses

Not applicable.

12.0 Interim Analyses

Not applicable.

12.1 Data Monitoring Committee

An external DMC will be established to safeguard the interest of trial subjects by assessing the safety of the interventions during the trial and well as for monitoring the integrity and interpretability of the trial.

A separate DMC charter describes the roles and responsibilities of the DMC members, frequency of data reviews, relevant data to be assessed, and general operations.

Since there are no efficacy analyses for early stopping, no alpha adjustment is needed.

An internal independent glucocorticoid adjudication committee will be established to adjudicate systemic glucocorticoid AEs. A separate charter describes the roles and responsibilities of the adjudication committee members, frequency of data reviews, and expectations for blinded communications.

13.0 Overall Type-I Error Control

Overall Type-I error control for multiple comparisons is not planned in this Phase 2b study.

Since there are no efficacy analyses for early stopping planned for the DMC review and IERC review, no alpha spending is needed due to analyses for the DMC review and the IERC review.

14.0 Version History

Table 4. SAP Version History Summary

Version	Date	Summary
1.0	04 August 2021	Original version
2.0	17 August 2022	
 • Updated to reflect protocol version 2 changes, including: 
 ○ Removal of intercurrent events ○ Addition of LTE Period 2 ○ ITT population now requires at least 1 dose of study treatment • Changed categories for some baseline demographics/characteristics • Added summary of prior and concomitant DMARD, in addition to all medications • Added logistical problems (geo-political restrictions) to NRI-MI, in addition to COVID-19 • Changed Observed Cases long-term efficacy to As Observed • Changed categories for efficacy and safety subgroup analyses for baseline glucocorticoid dose • Clarified treatment emergence definition for adverse events • Changed Safety Topics of Interest to Adverse Events of Special Interest • Clarified Potentially Clinical Important criteria for labs and vital signs • Corrected Hy's Law cases • Clarified included variables in vital signs analysis • Added details for DXA analysis

Appendix A. Protocol Deviations

The number and percentage of subjects who reported at least one of the following protocol deviation categories will be provided.

- Subject entered into the study even though s/he did not satisfy entry criteria.
- Subject developed withdrawal criteria during the study and was not withdrawn.
- Subject received wrong treatment or incorrect dose of study.
- Subject took prohibited concomitant medication.

Appendix B. Potentially Clinically Important Criteria for Safety Endpoints

The PCI criteria for selected laboratory variables are described in Table B1 instead of using NCI CTC.

Table B1. Potentially Clinically Important Criteria for Selected Laboratory Values

Laboratory Test	Category
HbA1c	< 6.5%
	≥ 6.5% to < 8%
	≥ 8%
HDL	< 1.03 mmol/L
	≥ 1.03 mmol/L
LDL	< 3.36 mmol/L
	≥ 3.36 to < 4.14 mmol/L
	≥ 4.14 mmol/L

The PCI criteria for selected vital sign variables (pulse rate, body temperature, and respiratory rate) are described in Table B2.

Table B2. Criteria for Potentially Clinically Important Vital Sign Values

Vital Sign	Category	Criteria for Potential Clinically Important Vital Signs
Pulse	Low	Value ≤ 50 bpm and decrease ≥ 15 bpm from Baseline
	High	Value ≥ 120 bpm and increase ≥ 15 bpm from Baseline
Body temperature	High	> 39.0 degrees C (102.3 degrees F)
Respiratory rate	Low	< 10 breaths/min
	High	> 24 breaths/min

Appendix C. Random Seeds

In case of non-convergence, the random seed will be updated by adding 10000 at each attempt until convergence of model happens.

A. Random Seeds for NRI-MI

Endpoints	Random Seed	
	MCMC procedure	PROC MI
TJC68	10001	20001
SJC66	10002	20002
TJC28	10003	20003
SJC28	10004	20004
Patient's Assessment of Pain	10005	20005
Patient's Global Assessment of Disease Activity	10006	20006
Physician's Global Assessment of Disease Activity	10007	20007
HAQ-DI	10008	20008
hsCRP	10009	20009

B. Random Seeds for MI

Endpoints	Random Seed	
	MCMC procedure	PROC MI
TJC68	40001	50001
SJC66	40002	50002
Patient's Assessment of Pain	40005	50005
Patient's Global Assessment of Disease Activity	40006	50006
Physician's Global Assessment of Disease Activity	40007	50007
HAQ-DI	40008	50008
hsCRP	40009	50009

final inferences of the risk difference between each ABBV-154 group and placebo.

9.2.3 Handling of missing data in Continuous Endpoints

- **Mixed Model for Repeated Measures (MMRM):** The repeated measures analysis will be conducted using a mixed model including observed measurements at all visits. For the Placebo-Controlled Period, the mixed model includes the categorical fixed effects of treatment, visit and treatment-by-visit interaction, stratification factors at randomization [Baseline glucocorticoid (yes/no), number of prior failed b/tsDMARDs (1; 2 or more), and a combined prior anti-TNF failure/adalimumab use factor (prior anti-TNF failure with adalimumab use; prior anti-TNF failure without adalimumab use; no prior anti-TNF failure)], and the continuous fixed covariates of baseline measurement. For LTE periods, the mixed model includes the categorical fixed effects of treatment, visit and treatment-by-visit interaction, major stratum [baseline glucocorticoid use (yes/no) and prior adalimumab use (yes/no)], and the continuous fixed covariates of baseline measurement. An unstructured variance-covariance matrix (UN) will be used. If the model cannot converge, an appropriate covariance structure matrix (e.g., autoregressive (1) or compound symmetry) will be used. Parameter estimation is based on the assumption of data being missing at random and using the method of restricted maximum likelihood (REML).

MMRM will be the primary approach to the analysis of continuous variables

9.2.4 Summary of Long-Term Efficacy

Long-term efficacy in the LTE periods will be summarized using the As Observed case approach by treatment sequence (ABBV-154 40 mg EOW, ABBV-154 150 mg EOW, ABBV-154 340 mg EOW, ABBV-154 340 mg E4W, ABBV-154 150 mg EOW re-randomized from Placebo, ABBV-154 340 mg EOW re-randomized from Placebo).

- **As Observed (AO):** The AO analysis will be used for the summaries of long-term efficacy, which will not impute values for missing evaluations, and thus a

subject who does not have an evaluation on a scheduled visit will be excluded from the AO analysis for that visit.

- NRI-MI and MMRM will be used to summarize selected categorical and continuous efficacy variables, respectively, for long-term efficacy.

9.3 Primary Efficacy Endpoint(s) and Analyses

9.3.1 Primary Efficacy Endpoint(s)

The primary endpoint is the achievement of ACR50 at Week 12.

ACR criteria are commonly used standard criteria mentioned in the guidance of American College of Rheumatology to evaluate the effectiveness of investigation drug in RA clinical trials. It is a composite measurement calculated based on the improvement over a set of core measurements.

ACR50 is defined as at least 50% improvement (compared to baseline values) in tender and swollen joint counts and at least 50% improvement in 3 of the remaining 5 core set measures (patient's assessment of pain, patient's global assessment of disease activity, physician's global assessment of disease activity, HAQ-DI and hsCRP).

A subject will be classified as an ACR50 responder, if the following conditions are met:

1. $\geq 50\%$ improvement from baseline in tender joint count (TJC68) and
2. $\geq 50\%$ improvement from baseline in swollen joint count (SJC66) and
3. $\geq 50\%$ improvement from baseline in at least 3 of the following 5:
 - patient's assessment of pain (on a 0-10 NRS)
 - patient's global assessment of disease activity (PtGA) (on a 0-10 NRS)
 - physician's global assessment of disease activity (PhGA) (on a 0-10 NRS)
 - HAQ-DI
 - hsCRP

9.3.2 Analysis of Primary Efficacy Endpoint(s)

The statistical null hypothesis corresponding to the primary endpoint is that there is no difference between an ABBV-154 group and the placebo group response rate in the proportion of subjects achieving ACR50 at Week 12.

Analysis of the primary endpoint will be conducted in the ITT Population based on treatment as randomized using NRI-MI. Comparison of the primary endpoint will be made between each ABBV-154 group and the placebo group using the CMH test adjusting for Baseline glucocorticoid (yes/no), number of prior failed b/tsDMARDs (1; 2 or more), and a combined prior anti-TNF failure/adalimumab use factor (prior anti-TNF failure with adalimumab use; prior anti-TNF failure without adalimumab use; no prior anti-TNF failure)].

The attributes of the estimands corresponding to the primary efficacy endpoint are summarized in Table 1.

Table 1. Summary of the Estimand Attributes of the Primary Efficacy Endpoint(s)

Estimand Label	Attributes of the Estimand				Statistical Summary
	Treatment	Endpoint	Population	Handling of Intercurrent Events (IE)	
Primary: Composite Estimand	ABBV-154 vs. Placebo	Achievement of ACR50 at Week 12	All randomized subjects who received at least one dose of study drug (ITT Population)	IE: none considered	Difference between ABBV-154 and placebo in the proportion of subjects achieving ACR50 at Week 12

9.3.3 Sensitivity and Supplementary Analyses of the Primary Efficacy Endpoint(s)

A sensitivity analysis of the primary analysis of the primary efficacy endpoint will be conducted using the MI method for handling missing data.

An additional analysis will be conducted where the baseline definition for patient's assessment of pain, PtGA, PhGA, and HAQ-DI is updated to where values collected up to 7 days after the day of first dose may be considered for the baseline value.

A separate analysis may be performed in the ITT Population excluding subjects who have major protocol deviations in the Placebo-Controlled Period. The subject exclusion criteria for this analysis will be finalized before unblinding data for the Primary Analysis.

9.4 Secondary Efficacy Endpoints and Analyses

9.4.1 Secondary Efficacy Endpoints

The continuous secondary endpoints are, at Week 12,

- **Change in DAS 28 (CRP) from Baseline:** DAS28 (CRP) is a composite index to assess disease activity in RA patients using hsCRP measurement. The DAS28 (CRP) provides a score between 0.96 and 10, indicating how active the rheumatoid arthritis is at the time of measurement.
- DAS28 (CRP) is calculated based on Tender Joint Count, Swollen Joint Count, Patient's Global Assessment of Disease Activity (PtGA) (on a 0-10 NRS), and hsCRP (in mg/L).

$$\text{DAS28 (CRP)} = 0.56 \times \sqrt{\text{TJC28}^*} + 0.28 \times \sqrt{\text{SJC28}^{**}} + 0.36 \times \ln(\text{hsCRP}^{\&} + 1) + 0.14 \times \text{PtGA}^{\gg} + 0.96$$

* TJC28 refers to the Subject's total Tender Joint Count out of the provided 28 evaluated joints.

** SJC28 refers to the Subject's total Swollen Joint Count out of the provided 28 evaluated joints.

& hsCRP refers to the high-sensitivity C-reactive protein lab value. hsCRP unit in the DAS28 (CRP) equation is expressed as mg/L.

» PtGA refers to the Patient's Global Assessment of Disease Activity.

Where $\sqrt{}$ is square root and \ln is natural log.

- **Change in CDAI from Baseline:** CDAI is a composite continuous index to assess disease activity without using hsCRP measurement. It can be calculated based on TJC28, SJC28, Patient's Global Assessment of Disease Activity (PtGA) (on a 0-10 NRS) and Physician's Global Assessment of Disease Activity (PhGA) (on a 0-10 NRS). It can be derived as follows:
CDAI = TJC28 + SJC28 + PtGA + PhGA.
- **Change in the HAQ-DI from Baseline**

The categorical secondary endpoints are, at Week 12,

- **Achievement of ACR20 and Achievement of ACR70:** The definition is similar to ACR50 with at least 20% and 70% improvement, respectively
- **Achievement of LDA defined by DAS28 (CRP) ≤ 3.2**
- **Achievement of LDA defined by CDAI ≤ 10**
- **Achievement of clinical remission (CR) defined by DAS28 (CRP) < 2.6**
- **Achievement of CR defined by CDAI ≤ 2.8**

9.4.2 Analyses of Secondary Efficacy Endpoints

The statistical null hypothesis corresponding to the secondary endpoint is that there is no difference between an ABBV-154 group and the placebo group at Week 12 in terms of response rate for a categorical endpoint and change from baseline for a continuous endpoint.

Analysis of the secondary endpoint will be conducted in the ITT Population based on treatment as randomized. Comparison of the secondary endpoint will be made between each ABBV-154 group and the placebo group using:

- **For categorical variables:** CMH test based on NRI-MI adjusted by Baseline glucocorticoid (yes/no), number of prior failed b/tsDMARDs (1; 2 or more), and a combined prior anti-TNF failure/adalimumab use factor (prior anti-TNF failure with adalimumab use; prior anti-TNF failure without adalimumab use; no prior anti-TNF failure).

- For continuous variables: MMRM mentioned in Section 9.2

The attributes of the estimands corresponding to the key secondary efficacy endpoints are summarized in Table 2.

Table 2. Summary of the Estimand Attributes of the Secondary Efficacy Endpoints

For binary endpoint:

Estimand Label	Attributes of the Estimand				Statistical Summary
	Treatment	Endpoint	Population	Handling of Intercurrent Events	
Binary Secondary: Composite Estimand	ABBV-154 vs. Placebo	Achievement of each binary secondary endpoint respectively	All randomized subjects who received at least one dose of study drug (ITT Population)	IE: none considered	Difference in proportion of subjects achieving each binary secondary endpoint

For continuous endpoint:

Estimand Label	Attributes of the Estimand				Statistical Summary
	Treatment	Endpoint	Population	Handling of Intercurrent Events	
Continuous Secondary: Composite Estimand	ABBV-154 vs Placebo	Change from Baseline in each respective continuous secondary endpoint	All randomized subjects who received at least one dose of study drug (ITT Population)	IE: none considered	Difference in the mean change from Baseline in each continuous secondary endpoint

9.4.3 Sensitivity and Supplementary Analyses for Secondary Efficacy Endpoints

Not applicable.

9.4.4 Supportive Secondary Efficacy Endpoints and Analyses

Not applicable.

9.5 Additional Efficacy Analyses

The primary and all secondary efficacy variables will be analyzed at all visits assessed other than Week 12, including in the LTE periods, using methods mentioned above. At time of the Primary Analysis, NRI will be used after Week 12 for all binary endpoints.

In addition, other efficacy endpoints described in Section 3.3 will be analyzed at all visits assessed using the same methods as secondary endpoints.

9.6 Dose-Response Modeling for ABBV-154

The dose-response relationship among ABBV-154 dose groups and the placebo group will be characterized for the primary endpoint using the Multiple Comparison Procedure - Modeling (MCP-Mod) method [Pinheiro 2006, Bretz 2005]. The summary level response rates based on the primary analysis approach above will be used, and ADDPLAN DF software will be used to perform the MCP-Mod analyses.

A set of 6 pre-specified standardized candidate dose-response models, as described in Table 3 will be utilized to examine the dose-response relationship. A statistically significant dose-response relationship will be declared if at least one model is identified by the MCP-Mod method to be statistically significant at two-sided $\alpha = 0.1$. The fitted dose-response curves will be presented graphically for all statistically significant models along with 95% confidence bands. The minimum effective dose (MED) will be identified for each statistically significant model based on the pre-specified clinical meaningful target of 22%. The weighted MED across all significant models will be calculated, with weight being the inverse of each candidate dose-response model AIC.

Table 3. Candidate Models

Model	$f(d, \theta)$ $d = \text{dose},$ $\theta = \text{Model Parameters}$	$f^0(d, \theta)$ Standardized Model	Initial Value(s) for Parameter(s)*
Linear	$E_0 + \delta d$	d	NA
Exponential	$E_0 + E_1 \left[\exp\left(\frac{d}{\delta}\right) - 1 \right]$	$\exp\left(\frac{d}{\delta}\right) - 1$	$\delta = 680$
Logistic	$E_0 + \frac{E_{max}}{1 + \exp\left(\frac{ED_{50} - d}{\delta}\right)}$	$\frac{1}{1 + \exp\left(\frac{ED_{50} - d}{\delta}\right)}$	$ED_{50} = 150, \delta = 64.5$
EMax	$E_0 + \frac{E_{max}d}{ED_{50} + d}$	$\frac{d}{ED_{50} + d}$	$ED_{50} = 83.9$
sigEMax	$E_0 + \frac{E_{max}d^h}{ED_{50}^h + d^h}$	$\frac{d^h}{ED_{50}^h + d^h}$	$ED_{50} = 150, h = 3.6$
Quadratic	$E_0 + \beta_1 d + \beta_2 d^2$	$d + \frac{\beta_2}{ \beta_1 } d^2$	$\delta = -0.001$

* For Exponential model, the initial value was determined based on the assumption that ABBV-154 340 mg EOW will achieve 95% of the maximum efficacy of ABBV-154. For Logistic, EMax, sigEMax, and Quadratic model, the initial values were determined based on the assumption that ABBV-154 340 mg EOW and ABBV-154 140 mg EOW will achieve 95% and 50% of the maximum efficacy of ABBV-154, respectively.

Steps of MCP-Mod:

1. Choose a candidate set of models as in Table 3.
2. Compute the optimum contrast for each model.
3. Use contrast test to find all significant models while preserving family-wise error rate (FWER).
4. Use all significant models to make inference about the weighted target dose of interest.

9.7 Efficacy Subgroup Analyses

Subgroup analysis for the primary endpoint will be conducted by the subgroups specified below. The difference in the primary efficacy endpoint between the treatment groups in each subgroup will be assessed using CMH approach. Treatment difference and corresponding confidence interval will be used to summarize the result.

- Number of prior failed b/tsDMARDs (1; 2 or more)
- Prior anti-TNF failure (yes/no)
- Prior use of adalimumab (yes/no)
- Age (< median; ≥ median years)
- Sex (female; male)
- Race (white; non-white)
- Geographic region (North America, Asia, Rest of World)
- BMI (< 25, ≥ 25 - < 30, ≥ 30 kg/m²)
- Baseline glucocorticoid use (yes/no)

If any subgroup has fewer than 10% of the total subjects, then the analysis for this subgroup will not be performed.

10.0 Safety Analyses

10.1 General Considerations

Safety data will be summarized for each safety population (Safety_PC and ALL_154). Safety summaries will be presented by treatment group, including a total group for all subjects on active study drug. For the safety analysis, subjects are assigned to a treatment group based on the treatment actually received, regardless of the treatment randomized.

"Baseline" refers to the last non-missing observation before or on the day of the first administration of study drug or randomization if no study drug is given. Observations on the same day as the first administration of study drug will be considered for baseline,

regardless if observation time (if available) was after the first administration of study drug time.

10.2 Adverse Events

Adverse events (AEs) will be summarized and presented using primary MedDRA System Organ Classes (SOCs) and preferred terms (PTs) according to the version of the MedDRA coding dictionary used for the study at the time of database lock. The actual version of the MedDRA coding dictionary used will be noted in the AE tables and in the clinical study report. Specific adverse events will be counted once for each subject for calculating percentages, unless stated otherwise. In addition, if the same adverse event occurs multiple times within a subject, the highest severity and level of relationship to investigational product will be reported.

10.2.1 Treatment-Emergent Adverse Events

Treatment-emergent AEs are defined as any AE with the onset that is after the first dose of study drug and with an onset date no more than 5 half-lives of the study drug (i.e., 70 days). Events where the onset date is the same as the study drug start date are assumed to be treatment-emergent, unless the study drug start time and the AE start time are collected and the AE start time is prior to the study drug start time. All treatment-emergent AEs will be summarized overall, as well as by primary MedDRA SOC and Preferred Term. The SOCs will be presented in alphabetical order, and the PTs will be presented in alphabetical order within each SOC.

The number and percentage of subjects experiencing treatment-emergent AEs will be summarized.

In the ALL_154 population, treatment-emergent AEs are defined based on the first dose of ABBV-154.

10.2.2 Adverse Event Overview

An overview of AEs will be presented consisting of the number and percentage of subjects experiencing at least one event for each of the following AE categories:

- Any treatment-emergent AE
- Any treatment-emergent AE related to study drug according to the investigator
- Any severe (CTCAE grade ≥ 3) treatment-emergent AE
- Any serious treatment-emergent AE
- Any treatment-emergent AE leading to discontinuation of study drug
- Any treatment-emergent AE leading to death
- Adverse Events of Special Interest (formally known as Safety Topics of Interest)
- All deaths
 - Deaths occurring ≤ 70 days after last dose of study drug
 - Deaths occurring > 70 days after last dose of study drug.

The overview of AEs per 100 patient-years of exposure will also be provided for the above categories.

10.2.3 Treatment-Emergent Adverse Events by SOC and/or PT

Treatment-emergent adverse events will be summarized by SOC and PT; by maximum relationship to study drug as assessed by the investigator (e.g., reasonable possibility or no reasonable possibility) and SOC and PT; by maximum severity and SOC and PT; and by subject number and SOC and PT. Specific adverse events will be counted once for each subject for calculating percentages unless stated otherwise. In addition, if the same adverse event occurs multiple times within a subject, the highest severity and level of relationship to investigational product will be reported.

In addition, treatment-emergent adverse events will be summarized by PT and sorted by decreasing frequency for the total ABBV-154 group.

10.2.4 Treatment-Emergent Adverse Events per Patient-Years of Exposure

Exposure-adjusted AEs per 100 patient-years will be provided, where AEs per 100 patient-years of exposure are defined as the number of AEs divided by the total exposure in 100 patient-years. The study drug exposure is defined as the last dose date plus $5 \times$ half-life (70 days), minus the first dose date.

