Such an event can result from use of the drug as stipulated in the protocol or labeling, as well as from "special situations" such as accidental or intentional overdose, medication error, occupational or accidental exposure, off-label use, drug abuse, drug misuse, or drug withdrawal, all which must be reported whether associated with an AE or not. Any worsening of a pre-existing condition or illness is considered an AE. Worsening in severity of a reported AE should be reported as a new AE. Laboratory abnormalities and changes in vital signs are considered to be AEs only if they result in discontinuation from the study, necessitate therapeutic medical intervention, meets protocol-specific criteria (see Section 6.2 regarding toxicity management), and/or if the investigator considers them to be AEs.

The investigators will monitor each subject for clinical and laboratory evidence of AEs on a routine basis throughout the study. All AEs will be followed to a satisfactory conclusion.

An elective surgery/procedure scheduled to occur during a study will not be considered an AE if the surgery/procedure is being performed for a pre-existing condition and/or the surgery/procedure has been pre-planned prior to study entry. However, if the pre-existing condition deteriorates unexpectedly during the study (e.g., surgery performed earlier than planned), then the deterioration of the condition for which the elective surgery/procedure is being done will be considered an AE.

If any of the following events are reported, then the following supplemental report must be completed.

Event	Supplemental Report
Cardiac events Myocardial infarction or unstable angina Heart failure Cerebral vascular accident and transient ischemic attack Cardiovascular procedures (SAE Supplemental Procedure eCRF)	MACE eCRF
Discontinuation or interruption of study drug due to a hepatic-related AE A hepatic-related SAE ALT/AST > 8 × ULN or ALT/AST > 3 × ULN with a total bilirubin > 2 × ULN	Hepatic eCRF
Renal impairment Renal dysfunction Renal failure Serum creatinine >1.5 x the Baseline value and >ULN	Renal eCRF
Adrenal insufficiency	Adrenal insufficiency eCRF
COVID-19 infection	COVID-19 eCRF

AE = adverse event; ALT = alanine aminotransferase; AST = aspartate transaminase; eCRF = electronic case report form; COVID-19 = coronavirus pandemic 2019; MACE = major adverse cardiac event; SAE = serious adverse event; ULN = upper limit of normal

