All adverse events reported from the time of study drug administration until 70 days after discontinuation of study drug administration will be collected, whether solicited or spontaneously reported by the subject. In addition, study procedure-related serious and nonserious adverse events will be collected from the time the subject signs the study-specific informed consent.

The following definitions will be used for Serious Adverse Reactions (SAR) and Suspected Unexpected Serious Adverse Reaction (SUSAR):

SAR Defined as all noxious and unintended responses to an investigation medicinal product (IMP) related to any dose administered that result in an SAE as defined above.

SUSAR Refers to individual SAE case reports from clinical trials where a causal relationship between the SAE and the IMP was suspected by either the sponsor or the investigator, is unexpected (not listed in the applicable Reference Safety Information) and meets one of the above serious criteria.

AbbVie will be responsible for SUSAR reporting for the Investigational Medicinal Product (IMP) in accordance with global and local requirements.

Adverse events will be monitored throughout the study to identify any of special interest that may indicate a trend or risk to subjects.

Safety Topics of Interest

The following safety topics of interest will be monitored during the study:

- Serious infections;
- Opportunistic infections;
- Active TB;
- Serious allergic reactions;
- Hypersensitivity reactions;
- Malignancies;
- Systemic glucocorticoid side effects;
- Adrenal insufficiency; and
- Iatrogenic Cushing's Syndrome.

Adverse Event Severity and Relationship to Study Drug

The investigator will rate the severity of each AE according to the National Cancer Institute Common Terminology Criteria for Adverse Events (NCI CTCAE Version 5.0).³

The investigator will use the following definitions to assess the relationship of the AE to the use of study drug:

Reasonable Possibility	After consideration of factors including timing of the event, biologic plausibility, clinical judgment, and potential alternative causes, there is sufficient evidence (information) to suggest a causal relationship.
No Reasonable Possibility	After consideration of factors including timing of the event, biologic plausibility, clinical judgment, and potential alternative causes, there is insufficient evidence (information) to suggest a causal relationship.

Pregnancy

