7.5 Statistical Analyses for Safety

All safety analyses will be performed based on the Safety Population, as defined in Section 7.1. Subjects will be analyzed based on the actual treatment received. Treatment-emergent adverse events (TEAEs), laboratory assessments, and vital signs will be summarized. Key safety variables will also be summarized on the ALL_154 Population.

A TEAE for the Safety Population is defined as an AE newly occurred or worsened after the first dose of study drug and within 70 days after the last dose of study drug. The number and percentage of subjects experiencing TEAEs will be tabulated using the MedDRA system organ class and Preferred Term, by severity, and by relationship to the study drug as assessed by the investigator. Summaries (including percentages and events per 100 patient years) of SAEs, deaths, and AEs leading to discontinuation will be provided as well. Pre-treatment AEs will be summarized separately.

For selected laboratory parameters, a listing of all subjects with any laboratory value \geq Grade 3 of the Common Toxicity Criteria will be provided. Mean change in laboratory and vital signs variables will be summarized. Additional details for the safety analysis are provided in the SAP.

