10.2.6 Adverse Events of Special Interest

Adverse Events of Special Interest (AESI, formerly known as Safety topics of interest) will be summarized by SOC and PT and will be based on standardized or company MedDRA queries (SMQs or CMQs), or based on adjudication results. AESIs to be summarized will follow those indicated in the latest version of the Product Safety Statistical Analysis Plan (PSSAP) for ABBV-154 in the AESI/Safety Topics of Interest section. Detailed information about search criteria for the AESIs are also provided in a table in the same section.

Tabular listings of AESIs will be provided.

In addition, the event rate per 100 patient-years of exposure will also be provided by SOC and PT for each AESI.

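### AE rates per 100 patient-years count each recorded worsening as a further event, and the SAP has no rule that merges the records of one illness

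*SAP*

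**What the plan says.** - **Numerator.** SAP 10.2.4: "AEs per 100 patient-years of exposure are defined as the number of AEs divided by the total exposure in 100 patient-years". It is not limited to first events, distinct episodes or subjects with an event.
- **Denominator.** The same section: "The study drug exposure is defined as the last dose date plus" five half-lives (70 days), less the first dose date. It does not depend on how many AE records exist.
- **Recording rule.** Protocol 6.1: "Worsening in severity of a reported AE should be reported as a new AE". Grading uses a multi-step scale: "The investigator will rate the severity of each AE according to the National Cancer Institute Common Terminology Criteria for Adverse Events".
- **Treatment emergence.** Protocol 7.5: "A TEAE for the Safety Population is defined as an AE newly occurred or worsened after the first dose of study drug". SAP 10.2.1: "Treatment-emergent AEs are defined as any AE with the onset that is after the first dose of study drug". A worsening entered as a new AE after the first dose meets both definitions.
- **Limit on repeats.** SAP 10.2: "Specific adverse events will be counted once for each subject for calculating percentages, unless stated otherwise"; SAP 10.2.3 repeats this. A neighbouring sentence in both sections says that the highest severity and relationship are shown when an AE recurs in a subject.
- **Use of the rates.** They are planned for every category of the AE overview (SAP 10.2.2), for SAEs and TEAEs leading to discontinuation (SAP 10.2.5), and for AESIs (SAP 10.2.6: "In addition, the event rate per 100 patient-years of exposure will also be provided by SOC and PT for each AESI").

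**The concern.** A reader of an event rate per 100 patient-years will normally take it as the frequency of separate illnesses. Under these two rules it also counts severity steps. An illness first recorded at its peak grade adds one event. The same illness recorded as it climbs adds two or three over the same exposure.

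These rates are the only exposure-adjusted AE measure in the SAP; no first-event incidence rate is planned. They matter most in the ALL_154 population, where exposure is unequal by design. Placebo subjects begin ABBV-154 only at Week 12, at one of two regimens, and subjects classed as non-responders stop study drug from Week 30. Crude percentages are harder to compare there, so readers will lean on the rates.

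**Working it through.** The documents state no AE rate, expected AE count or escalation frequency, so there is no plan figure to reproduce. The check is of the counting rule; the sizes are illustrations under stated assumptions.

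**1. Does any SAP rule merge records?** In SAP 10.2 to 10.2.6, the once-per-subject rule is confined to percentages. The highest-severity sentence says which grade and relationship to show for a repeated AE, not that the records count as one. Nothing links or merges records.

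**2. Records counted for one illness, all treatment-emergent:**

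| Grades recorded | All TEAEs | Severe (grade ≥ 3) |
|---|---|---|
| 4 only | 1 | 1 |
| 1, 2 | 2 | 0 |
| 1, 2, 3 | 3 | 1 |
| 2, 3, 4 | 3 | 2 |
| 3, 4 | 2 | 2 |

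The overall count is 1 + the number of escalations. A filtered category counts only the records that carry its flag.

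**3. Overall inflation.** Multiplier = 1 + f×k, where f is the share of illnesses that escalate and k the mean extra records for each. Both are assumed.

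- f = 5%, k = 1: 1.05
- f = 10%, k = 1: 1.10
- f = 20%, k = 1: 1.20
- f = 20%, k = 2: 1.40
- f = 30%, k = 2: 1.60

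**4. Comparison of arms with equal numbers of illnesses.** The rate ratio is the ratio of the multipliers. Equal escalation gives 1.00. If 25% escalate once in one arm and 10% in the other, it is 1.25/1.10 = 1.14. The two ends of the range in step 3 give 1.60/1.05 = 1.52.

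**5. Placebo-controlled period.** About 85 subjects per arm (Protocol 7.10), all assumed to have their last dose of the period at Week 10, give 70 + 70 = 140 days each.

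- Exposure: 85 × 140 / 365.25 = 32.6 patient-years.
- Each extra record adds 100/32.6 = 3.1 per 100 patient-years.
- If exposure were instead cut at Week 12 (84 days), it would be 19.5 patient-years, and each extra record would add 5.1.
- With a hypothetical 100 illnesses in an arm, the rate is 306.9 without duplicates, 337.6 if 10% escalate once, and 429.7 if 20% escalate twice.
- Rare-event extreme: three serious infections give 3/32.6 = 9.2 per 100 patient-years. If one is entered as three serious records, five records give 15.3, an increase of 67%.

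**6. ALL_154.** Dosing runs to Week 180 (Protocol Appendix E), which is 1,260 days. With full retention, an upper bound, 85 × (1,260 + 70) / 365.25 = 309.5 patient-years. At 9.2 per 100 patient-years that is about 28 events, so two extra records add about 7%. At half that exposure they add about 14%.

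**The case against.** The strongest reply is that the SAP counts the unit the protocol defines. Protocol 7.5 treats a worsened AE as treatment-emergent and itself asks for events per 100 patient-years for SAEs, deaths and AEs leading to discontinuation. On that view a worsening is an event, and a dose with more escalation has a real safety difference. The subject percentages and the maximum-severity table (SAP 10.2.3) would help a reader separate incidence from progression. SAP 10.2 also attaches no test, interval or decision rule to the rates.

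Much of this stands. The two documents do not contradict each other, and a rate ratio above 1 caused by escalation is not false; it mixes two quantities. What remains is that the SAP does not tell the reader which unit is counted. The highest-severity sentence could also lead one programmer to merge repeats and another not to, giving different rates from the same data.

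Two further limits are fair. AESIs are selected under the Product Safety Statistical Analysis Plan or by adjudication (SAP 10.2.6), and AE recording details sit in the Operations Manual. Neither is supplied, so the absence of a merging rule can be asserted only for the SAP text. And one record will usually carry the discontinuation or fatal outcome, so those rates may hardly move.

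**Conclusion.** The point holds for the overall and SOC/PT event rates. As written, an illness that escalates k times counts 1 + k times, and absolute rates are inflated as a measure of distinct illnesses by 1 + f×k: 1.05 to 1.60 for f of 5–30% and k of 1–2. Those inputs are assumptions, so the true inflation cannot be fixed from the documents.

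A reader might infer three stronger things that the documents do not support:

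- **That every planned rate is doubled or tripled.** Severe, serious and discontinuation rates change only when more than one record carries the flag, AESI counting may be governed elsewhere, and percentages do not change.
- **That comparisons between arms are distorted in any case.** That requires escalation to differ by arm.
- **That one subject can move a rare rate by two thirds wherever it is reported.** The 67% figure belongs to the short placebo-controlled period and needs three serious records for one illness. In ALL_154 the same two extra records add about 7% with full retention.

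No efficacy conclusion is at stake. This is a gap in a safety definition that is worth closing because closing it is cheap.

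**What to change.** In SAP 10.2.4, state that the numerator counts episodes, with these rules:

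- Within a subject, and among treatment-emergent records only, merge contiguous records of the same preferred term when the later one is a rise in severity of the earlier one. Confining the merge to treatment-emergent records keeps a post-dose worsening of a pre-dose event in the count.
- Keep the earliest onset and the highest severity, seriousness and relationship.
- Do not merge same-grade records, which may be distinct events.
- State how missing end dates are handled.

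Beside each event rate, give the exposure-adjusted incidence rate with a 95% CI: subjects with a first event divided by time to first event or censoring. Duplicate records do not affect it, so it stays usable even if the merging rule is disputed.

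The cost is SAP wording and slightly more programming on AE dates already collected; sites change nothing. Two weaknesses remain. A true new, more severe episode that starts immediately after an earlier one would occasionally be merged, and an escalation coded to a different preferred term would still count twice.
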